8.9.7. Microbiology

Microbiological success is assessed by clearance of infection, which is defined as eradication of all baseline pathogens.

The number and percentage of subjects with microbiological success will be tabulated descriptively by treatment group and time point. The difference in proportion of microbiological success between each treatment dose group and placebo group and the corresponding 95% exact confidence intervals for the difference will be presented. The Exact confidence interval will be calculated using the Clopper Pearson method.

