Procedure	Screening	Baseline/ Day of Surgery		Hour 48- 60	Hour 72	Hour 96	Week 2	Week 6	Week 12, EOT	Early Term / Tx Failure
		Day 1	Day 2	Day 3	Day 4	Day 14 ±4 days	Day 42 ±8 days	Day 84 ±8 days		
Review of eligibility criteria	X	X								
Informed consent	X									
Randomization		X								
Surgery/Administration of the Investigational Product		X								
Medical history	X									
Physical exam	X									
Interval physical exam		X	X				X	X	X	X
Hematology	X		X				X	X	X	X
Serology		X					X	X	X	X
Serum chemistry	X		X				X	X	X	X
Urinalysis	X		X				X	X	X	X
Pregnancy test	X	X							X	X
BisEDT Blood levels ¹		X	X	X	X	X				
12-lead ECG	X	X	X						X	X
Vital signs	X	X	X	X	X	X	X	X	X	X
Patient-reported outcomes ²	X						X	X	X	X
Surgical site signs and symptoms		X	X	X	X	X	X	X	X	X
Surgical site pain score		X	X	X	X	X	X	X	X	X
Microbiology		X	(X) ³			(X)	(X)	(X)	(X)	(X)
Radiographic evaluation		X				X	X	X	X	X
Concomitant medications	X	X	X	X	X	X	X	X	X	X
Adverse events		X	X	X	X	X	X	X	X	X

¹ PK blood samples will be collected pre-dose and at nominal 1, 6, 12, 24, 36, 48 (Day 2), 60, 72 (Day 3), 96 (Day 4) and 336 (Day 14; Week 2) hours after administration of the investigational product

² Patient-reported outcomes include the Veterans Rand 12 Item Health Survey (VR-12) and Short Musculoskeletal Function Assessment (SMFA)

³ Microbiology will be performed at any time that a new surgical intervention is required.

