5.1.2. Serious Interventions

All interventions meeting the following criteria are serious interventions:

- Initiation of antibiotic treatment in patient not previously on antibiotics
- Change in the route of antibiotic administration from oral to intravenous for escalation of treatment
- Change in the type or dosage of antibiotic drug for escalation of treatment
- Readmission (exclusive of readmissions associated with a healed bone site)
- Reoperation (exclusive of reoperations associated with a healed bone site)

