5.1.3. Microbiology

The microbiology of the index site will be assessed at baseline and at the time of any subsequent surgical procedure at the index site. The presence of viable microorganisms will

be determined by standard microbiological culture methods and include speciation and antimicrobial susceptibility testing of any bacterial isolates found.

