5.1.3.1. Specimen Collection

Samples collected will include at least one tissue site (bone when possible; eraser head size, suitable for dividing into two samples) from the infected bone site (if accessed) or involved tissue adjacent to any implant(s), two swabs of the deep infection site, and two swabs of the superficial tissue/wound closure/sinus tract site. One set of specimens (i.e. 1 tissue specimen, 1 deep swab, 1 superficial swab) will be placed into local site transport vessels. The duplicate set of samples will be placed into transport vessels provided by the central laboratory (International Health Management Associates, Inc.; IHMA). One set of specimens will be delivered to the local site microbiology laboratory using the standard storage and transport procedures employed at each site. The duplicate set of specimens will be transported to IHMA.

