8.2. Handling of Dropouts/Missing Data

For the efficacy endpoint, proportion of treatment failures, subjects who discontinued from the study or died by week 12 will be considered as treatment failures for the efficacy analysis.

For the missing data of SMFA, in the case of the dysfunction index, unanswered items in a category are replaced by the individual's mean score for that category, as long as more than 50 percent of the items in that category have been answered. If $\leq 50\%$ of the items in that category have been answered, the missing data will not be imputed.

In the cases of missing or incomplete dates (e.g. AE and concomitant medications), the missing component(s) will be assumed as the most conservative value possible. For example, AEs with missing start dates, but with stop dates either overlapping into the treatment period or missing, will be counted as treatment-emergent, taking the worst-case approach. When partial dates are present in the data, both a partial start date and/or a partial stop date will be evaluated to determine whether it can be conclusively established that the AE started prior to the start of study drug or ended prior to the start of study drug. If the above cannot be conclusively established based on the partial and/or present dates, then the AE will be considered as treatment-emergent. Actual data values as they appear in the original case report forms (CRFs) will be presented in the data listings.

Missing values for other variables will not be imputed and only observed values will be used in data Analysis and summaries.

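### Microbiological success is to be reported as a percentage by time point, but after baseline only re-operated subjects are cultured, so the percentage misstates clearance on either possible denominator

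*SAP*

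**What the plan says.** On the analysis, SAP section 8.9.7 defines the outcome: "Microbiological success is assessed by clearance of infection, which is defined as eradication of all baseline pathogens". It then plans the table: "The number and percentage of subjects with microbiological success will be tabulated descriptively by treatment group and time point". A comparison follows, which the section says will be presented: "The difference in proportion of microbiological success between each treatment dose group and placebo group and the corresponding 95% exact confidence intervals". The section gives no denominator and no rule for a subject without a repeat culture. It does not require that the subject had a pathogen at baseline.

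On data collection, section 5.1.3 states: "The microbiology of the index site will be assessed at baseline and at the time of any subsequent surgical procedure at the index site". In Table 1 the post-baseline microbiology cells are bracketed, and footnote 3 says: "Microbiology will be performed at any time that a new surgical intervention is required". Section 5.1.3.1 describes specimens of an operative kind: a tissue sample, from bone where possible, plus "two swabs of the deep infection site, and two swabs of the superficial tissue/wound closure/sinus tract site".

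On missing data, section 8.2 has special rules for treatment failure, SMFA items and incomplete dates. Microbiology falls under the remainder: "Missing values for other variables will not be imputed and only observed values will be used in data Analysis and summaries". Section 8.9, however, bases every efficacy analysis on the mITT Population.

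**The concern.** The table in section 8.9.7 is laid out as if every subject were cultured at every visit. Under the collection rules, a post-baseline result exists only for a subject who has further surgery at the index site. Further surgery is itself an outcome that arises after randomisation. Under section 5.1.2 a reoperation is a serious intervention unless it is linked to a healed bone site. Under section 6.2 a site that fails to heal or worsens and needs a serious intervention is a treatment failure. Whether a subject has data therefore depends on how the subject fared.

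Clinical activity is a secondary objective, and microbiological findings are a named endpoint for an antimicrobial product. As planned, the report could carry percentages and intervals that look like clearance rates but do not estimate clearance in any arm. Because the denominator is open, two programmers could also produce different tables from the same data.

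**Working it through.** The SAP states no figure for microbiological success, re-operation or eradication, so there is nothing of its own to reproduce. The group sizes come from the SAP (6 per dose, 6 pooled placebo; section 8.1). Every rate below is an assumption, shown over a range. Culture results are taken as correct.

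**1. Who has a post-baseline culture.** Three sections decide this:
- Subjects re-operated at an unhealed site are cultured (5.1.3).
- Subjects whose hardware is removed because the bone has healed also have index-site surgery (an outcome listed in 6.2), so they can yield a culture without being failures on that account.
- Failures managed by an antibiotic change, or by readmission without surgery (5.1.2), yield none.

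The cultured set is therefore mainly, not only, treatment failures, and it is selected by outcome.

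**2. How many are cultured.** With re-operation rate r by Week 12, the expected number per group is 6r. The chance that a group has none is (1 − r)^6. The chance that all four groups have at least one is [1 − (1 − r)^6]^4.

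| r | Cultured of 6 | Group has none | All four groups have at least one |
|---|---|---|---|
| 10% | 0.6 | 53% | 5% |
| 20% | 1.2 | 26% | 30% |
| 30% | 1.8 | 12% | 61% |
| 40% | 2.4 | 5% | 83% |

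These counts cover all 12 weeks, and splitting by time point thins them further. With 1 success in 2 cultured subjects, the single-group Clopper-Pearson interval runs from 1.3% to 98.7%.

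**3. Level under observed values only.** Let e be true eradication, a the re-operation rate if infection persists, and b the rate if it is eradicated. Success among cultured subjects is e·b / [e·b + (1 − e)·a]. Take a = 60%.

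| True e | Seen if b = 5% | Seen if b = 20% |
|---|---|---|
| 60% | 0.03/0.27 = 11% | 0.12/0.36 = 33% |
| 80% | 0.04/0.16 = 25% | 0.16/0.28 = 57% |
| 90% | 0.045/0.105 = 43% | 0.18/0.24 = 75% |

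If a = b the formula returns e, so on this reading the bias vanishes only when re-operation is unrelated to eradication.

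**4. Level with all mITT subjects as denominator.** Only cultured eradications count, so the rate seen is e·b. A true 80% gives 0.80 × 0.05 = 4% or 0.80 × 0.20 = 16%. This understates clearance even if a = b, because uncultured eradications are lost.

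**5. The difference from placebo.** On the observed-only reading with a = 60%, true rates of 60% and 80% (20 points apart) give:
- b = 5%: 25.0 − 11.1 = 13.9 points.
- b = 20%: 57.1 − 33.3 = 23.8 points.

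If both groups truly have 80% but b is 5% in one and 20% in the other, a gap of 57.1 − 25.0 = 32.1 points appears where none exists. With the mITT denominator and b = 5%, 60% and 80% become 3% and 4%, a gap of 1 point. The planned difference can shrink, grow or arise from nothing, depending on rates that the SAP does not give.

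**The case against.** The strongest case on the other side has four parts.

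- **Selection is not the same as failure.** A reader might infer that the rate is computed purely among failures and that a healed subject is never cultured. The SAP does not support this. Healed-site surgery can give a culture, and failures treated without surgery give none. That part of the objection stands. It narrows the point without removing it, since the set is still selected by outcome.
- **The denominator is not stated.** The observed-only reading is the likelier one under section 8.2, but section 8.9 also permits mITT. This stands too, and it is why both readings were checked. Both misstate the level.
- **There is a general safeguard.** Section 8.1 presents differences and intervals only where the data permit. That would justify omitting a comparison with too few cultures. It addresses sparseness, not selection, and sets no denominator. Sections 8.9.1 and 8.9.2 repeat the condition, whereas 8.9.7 says that the difference will be presented.
- **Distorted levels need not distort the difference.** Assume true rates of 70% on placebo and 90% on active, with re-operation in 80% of persistent and 5% of eradicated infections. Cultured subjects then show 0.035/0.275 = 12.7% and 0.045/0.125 = 36.0%. The gap is 23.3 points against a true 20. A reader might infer that the plan biases the comparison in a known direction or by a known amount, and the document does not support that. What remains is that the subsets are not randomised and that the error in the difference cannot be known in advance.

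The weight should also stay modest. The primary objective is safety, and there is no formal hypothesis. Microbiology is one of eleven clinical-activity endpoints in section 6.2. The DRC charter provides microbiology only on request, and as line listings.

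**Conclusion.** The concern holds in this form: the percentage planned in section 8.9.7 does not estimate clearance of infection on either denominator that the SAP allows. With observed values only, it describes a small subset selected by outcome, and the dose-placebo comparison loses the protection of randomisation. The level is right only if re-operation is unrelated to eradication. With all mITT subjects, healed uncultured subjects count against success.

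Under the assumed rates, 0.6 to 2.4 of 6 subjects per group supply a culture, and a true 80% appears as 25% to 57% among them. These figures show scale and are not predictions.

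The lack of a baseline-pathogen condition is a smaller, related gap. A culture-negative subject satisfies the definition trivially, although section 8.6 already limits the baseline-pathogen table to subjects with a pathogen.

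This should be fixed. A reader might infer that it undermines the trial's conclusions, but the document ties no trial decision to this percentage and the primary safety analysis is untouched.

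**What to change.** Amend section 8.9.7 as follows.

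- Restrict the analysis to mITT subjects with at least one baseline pathogen, so that culture-negative subjects cannot count as successes.
- Report once, by Week 12 and by treatment group, the counts with documented eradication, documented persistence and no post-baseline culture. State which culture governs when a subject has several.
- List all unscheduled cultures by subject, with the reason for surgery if recorded.
- Drop the by-time-point percentages and the between-group difference with its interval.

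If presumed eradication or persistence is added for uncultured subjects, show it separately and label it as derived from clinical outcome. Class subjects who discontinued or died for reasons other than infection as indeterminate. Section 8.2 counts every discontinuation and death by Week 12 as a treatment failure, so a presumed category built directly on that variable would largely repeat treatment failure under a microbiological name. For the same reason, no interval should rest on the presumed categories alone.

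The cost is SAP wording and a derived variable, mainly from data already collected. The downside is small: documented cultures will not yield a single clearance rate with an interval. The endpoint in section 6.2, the findings of microbiology evaluations, is still reported.

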8.9.8. Radiographic Evaluation

Radiographic success is assessed by healing on radiographic examination.

The number and percentage of subjects with radiographic success will be tabulated descriptively by treatment group and time point.

8.9.9. Serologic Markers

Serologic marker CRP and ESR values and the change from baseline for each scheduled visit will be summarized with descriptive statistics by treatment group.

The number and percentage of subjects with normal, abnormal clinically significant, and abnormal not clinically significant for each serologic marker will be tabulated by treatment group at each scheduled visit.

8.9.10. Subgroup Analysis for Treatment Failure

If data permit, the following selected subgroups may be performed for subgroup analysis of treatment failure.

1. Area of the infected site
2. Method of fracture fixation
3. Type of infection (per identified microorganism)
4. Anatomic location of the surgery site
5. Hardware retention status (retained vs. exchanged)
6. Type of injuries
7. Method of wound closure
8. Osteomyelitis vs. non-osteomyelitis

rg i g

All safety Analysis will be presented using descriptive statistics and the Safety Population. No inferential statistics will be reported.

8.10.1. Adverse Events

A treatment-emergent adverse event (TEAE) is defined as any AE starting after the first dose of the investigational agent or placebo is administered. If the AE is present prior to the administration of the first dose of the investigational agent or placebo but increases in severity, it will also be considered a TEAE.

An overview of adverse events will be provided which summarizes the number and percentage of subjects and the number of events for the following:

- All TEAEs,
- Drug-related TEAEs,
- Maximum severity of TEAEs,
- Deaths,
- Serious adverse events (SAEs), and
- Discontinuation due to AEs.

The number and percentage of subjects with at least one TEAE will be presented by system organ class and preferred term. Drug-related TEAE, all SAEs and all AEs leading to study discontinuation, pre-specified local TEAEs will be summarized in the same manner. In the case of multiple occurrences of the same AE within the same subject, each subject will be counted only once for each SOC and preferred term.

Summaries will be provided by maximum severity and relationship to study drug for the number and percentage of subjects with TEAEs by system organ class and preferred term. Maximum severity for pre-specified local TEAEs will be summarized in the same manner. For this summary, subjects with multiple adverse events will be counted only once by the maximum severity within an SOC and preferred term.

Subject listings of SAEs and of AEs causing discontinuation of the study will be provided. All adverse events will be listed.

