3. STUDY DESIGN

3.1. General Study Design and Plan

This is a randomized, single-blind, placebo-controlled multi-center study to assess the safety and tolerability of escalating doses of MBN-101 applied directly to target structures within infected osteosynthesis sites during revision surgery with or without hardware removal and replacement for patients diagnosed with an apparent fracture site infection or to sites of chronic or acute-on-chronic osteomyelitis of the long bone extremities or residual amputated limbs. Three successive cohorts of 8 patients will be enrolled in this trial. Consecutive patients from each of the study sites will be screened for potential participation as they present to the orthopedic service for clinical care for their infections. Patients meeting all eligibility criteria on screening will be offered participation in the study.

Following baseline evaluation, patients will receive standard of care treatment for their postoperative fracture site infection or osteomyelitis that includes systemic antibacterial treatment per institutional standard of care guidelines and debridement/revision surgery with or without hardware removal and placement/replacement as indicated. A single application of MBN-101 or placebo, applied intraoperatively directly to target structures within infected bone sites, will be performed following the final irrigation and debridement procedure and immediately prior to definitive closure. In cases where original hardware is retained, MBN-101 will be applied to all accessible surfaces of hardware and adjacent bone (target structures). In cases where hardware is placed or replaced, or in cases of two-stage procedures, MBN-101 will be applied to all accessible surfaces of hardware and adjacent

bone (target structures) following implantation of hardware and immediately prior to definitive closure. In cases where hardware is not required, MBN-101 will be applied to affected areas of bone only prior to definitive closure. If wounds are left open, the investigational product will be applied immediately prior to definitive closure. The minimum amount of MBN-101 required to achieve a thin coat of the relevant target structures within the infected bone site will be used.

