Patients will be randomized 3:1 (active:control) to three successive doses (0.025, 0.075, or 0.25 mg/mL w:v) of MBN-101 (up to 8 mL, for a dose of up to 0.2, 0.6, or 2.0 mg, respectively) or placebo (diluent). Enrollment to the next dose cohort will not commence until an evaluation by the Data Review Committee (DRC) of all available safety data on all patients through Week 6 of study supports escalation to the next cohort.

PK assessments will be performed predose and at nominal 1, 6, 12, 24, 36, 48 (Day 2), 60, 72 (Day 3), 96 (Day 4), and 336 (Day 14; Week 2) hours after administration of study drug.

Patients will undergo study visits at Hour 48 and Weeks 2, 6 and 12. All patients will be followed for a total of 12 weeks after surgery.

I kg **P**

Twenty-four adult male or female patients meeting protocol-specified eligibility criteria may participate in the study, with the objective of having a total of 6 patients per dose level in the MBN-101-treated group and 6 patients in a pooled placebo-treated group.

I g g

Subjects will be randomized in a 3:1 (active:placebo) ratio up to 24 hours prior to surgery via a central randomization scheme.

I g g

This study is a single blind study; however, knowledge of treatment assignment should remain limited to those directly involved with the patient's surgical procedure and other individuals on a need to know basis. In order to provide unblinding data in an emergency in the absence of an individual privy to treatment assignment, sites will be provided with a numbered unblinding envelope corresponding to each numbered test kit the site is delivered. These envelopes will be securely stored in the pharmacy. The unblinding envelope specifies the treatment group of the kit and should only be opened when absolutely necessary. For treatment of adverse events, it should be assumed that the patient has received study drug, thus avoiding the need to unblind the patient. However, in the event the Investigator determines the randomization assignment information is required to treat the patient for an adverse event, the Medical Monitor should be contacted. If the Medical Monitor cannot be reached, the blind may be broken by opening the envelope. The site should document the unblinding process in the patient's source documents.

I g g **P**

[Table 1](#) presents the schedule of events of the study.

Table 1. Schedule of Events

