5.3.1. Adverse Events

An adverse event is an undesirable medical occurrence (sign, symptom, or diagnosis) or worsening of a pre-existing medical condition (e.g., diabetes) that occurs after initiation of the investigational study whether or not it is considered to be related to the investigational product. All adverse events (AEs) will be recorded throughout the study, beginning when the subject signs the Informed Consent Form. Adverse events will be coded using the Medical Dictionary for Regulatory Activities (MedDRA, Version 18.1).

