6. STUDY ENDPOINTS

6.1. Safety Endpoints

The safety and tolerability of locally administered MBN-101 will be assessed by:

- Treatment-emergent adverse events.
- Treatment-emergent serious adverse events.
- Changes in clinical laboratory tests (clinical chemistry, hematology, and urinalysis).

- Changes in vital signs (blood pressure, pulse, respiratory rate and body temperature).
- Changes in physical exams.
- Clinical findings of 12-lead electrocardiograms.

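### Section 6.1 names treatment-emergent SAEs as a safety endpoint, but section 8.10.1 plans only all-SAE tables, so no planned table reports that endpoint

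*SAP*

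**What the plan says.** SAP section 6.1 lists among the safety endpoints "Treatment-emergent serious adverse events".

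Section 8.10.1 defines a TEAE as "any AE starting after the first dose of the investigational agent or placebo is administered", and adds AEs already present before dosing that then worsen. The overview table uses the TEAE term for its first three lines (all, drug-related, maximum severity). It then drops the term for deaths, for SAEs (the line reads "Serious adverse events (SAEs), and") and for discontinuations. For the tables by system organ class and preferred term, the section says: "Drug-related TEAE, all SAEs and all AEs leading to study discontinuation, pre-specified local TEAEs will be summarized in the same manner".

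On timing, section 5.3.1 states: "All adverse events (AEs) will be recorded throughout the study, beginning when the subject signs the Informed Consent Form". Section 3 states: "Subjects will be randomized in a 3:1 (active:placebo) ratio up to 24 hours prior to surgery via a central randomization scheme". Section 3.1 places the single application after the final irrigation and debridement, covers two-stage procedures, and adds: "If wounds are left open, the investigational product will be applied immediately prior to definitive closure".

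Section 8.10 bases all safety analyses on the Safety Population, which section 7 limits to subjects who received study drug. Section 8.1 presents results by dose (6 subjects each), for the 18 active subjects combined, and for 6 pooled placebo subjects.

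**The concern.** The endpoint and the planned table cover different sets of events. The endpoint is limited to events that start or worsen after dosing. The table takes every SAE since consent in a dosed subject. An SAE during the wait for surgery, or between stages of a staged or open-wound procedure, cannot be caused by a product not yet applied. It would still appear in the SAE incidence of the treatment group.

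Groups of 6 make this visible, because a single subject can separate a group with no SAEs from one with a reported rate of about 17%. Section 4 also reasons from the case of zero observed events in 6 or 18 active subjects, so moving from zero to one changes what the trial can say.

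**Working it through.** **1. The text side by side.**

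| Item | Restricted to treatment-emergent events? |
|---|---|
| SAE endpoint, 6.1 | Yes |
| All TEAEs, drug-related TEAEs, severity, local TEAEs, 8.10.1 | Yes |
| SAEs in the overview, 8.10.1 | No |
| SAEs by system organ class and preferred term, 8.10.1 | No |
| Serious TEAEs, any table | None planned |

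The phrase about the same manner could be read as carrying the TEAE restriction over. But the same sentence sets the TEAE term for drug-related and local events against the word all for SAEs. The natural reading is the same layout, without the restriction.

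**2. The plan's own figures.** Section 4 gives rates of 0.385 (n = 6) and 0.153 (n = 18) as ruled out with 95% confidence when no event is seen. The exact one-sided bound is 1 − 0.05^(1/n):
- n = 6: 0.393. At the stated 0.385, the chance of at least one event is 1 − 0.615^6 = 0.946, close to the stated 95%.
- n = 18: 0.153, as stated.

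**3. Effect of one dosed subject with a pre-dose SAE, in a group with no other SAE.**
- Group of 6: incidence goes from 0% to 1/6 = 16.7%. The exact one-sided 95% upper bound goes from 0.393 to 0.582.
- Combined active, n = 18: incidence goes from 0% to 1/18 = 5.6%. The bound goes from 0.153 to 0.238.

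The one-event bound is the 95th percentile of a Beta(2, n − 1) distribution.

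**4. How likely this is.** The SAP gives no pre-dose SAE rate. Let q be an assumed probability of such an event per dosed subject. The chance of at least one among n subjects is 1 − (1 − q)^n:

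| Assumed q | n = 6 | n = 18 |
|---|---|---|
| 1% | 1 − 0.99^6 = 0.059 | 1 − 0.99^18 = 0.165 |
| 2% | 1 − 0.98^6 = 0.114 | 1 − 0.98^18 = 0.305 |
| 5% | 1 − 0.95^6 = 0.265 | 1 − 0.95^18 = 0.603 |

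These rates are illustrations and not estimates.

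**The case against.** The strongest reply is that the all-SAE table is the cautious choice. It contains every treatment-emergent SAE, so nothing serious is hidden, and over-inclusion fits the worst-case approach of section 8.2. Section 8.10 reports no inferential safety statistics. The SAE listing and the listing of all AEs let a reader trace each event. Pre-dose events can fall in the placebo group as well. All of this stands and limits the consequence. It does not supply a table of the endpoint that section 6.1 names.

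The window may also be narrower than it looks. Table 1 seems to mark adverse events only from Day 1, although the table may be damaged in extraction. That would conflict with section 5.3.1 and shorten the window. It would not close it, because Day 1 includes surgery before application.

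A reader might infer that every SAE during anaesthesia or debridement would leave the table once it is restricted. The SAP does not support that. Section 8.2 treats an AE as treatment-emergent when the available dates cannot settle that it began before study drug, and the SAP does not say that onset times are recorded. An SAE on the day of application may therefore stay in. The restriction mainly removes SAEs dated before the day of application.

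A reader might also see the wording on discontinuations as an equal defect. Section 6.1 lists no such endpoint, and subjects who leave before dosing are outside the Safety Population. Only an AE that starts before dosing, does not worsen and leads to withdrawal after dosing would be affected.

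**Conclusion.** The mismatch holds. A named safety endpoint has no matching table, and the table planned in its place can count pre-dose SAEs under a treatment group. The size is 16.7 percentage points per affected subject in a group of 6 and 5.6 points in the 18 combined active subjects. The probabilities of an occurrence rest wholly on the assumed rates and apply only to subjects who go on to be dosed.

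It would go too far to say that dose escalation is put at risk. The Data Review Committee charter provides raw listings and no aggregate tables, so escalation does not rest on this summary. Nor does the plan bias the comparison systematically against the active product, since placebo subjects are tabulated by the same rule. The point should be corrected because it touches the primary objective and costs little, but its likely effect is on the clarity of the final report.

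**What to change.** In section 8.10.1, specify treatment-emergent SAEs in the overview and in the tables by system organ class and preferred term. Show SAEs with onset before dosing separately, flagged in the SAE listing already planned. An all-SAE table may be kept in addition, labelled as such. State how an SAE with onset on the day of application is classified when its time relative to application is unknown. The discontinuation wording can be aligned for consistency, with little effect on results.

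The cost is a few lines of SAP text and one filter on a flag already derived for the TEAE tables. No new data are needed.
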